Za	2.576
Zb	1.282

For this research question a total of 60 subjects will be required, 30 for each group under study.

2. For the second outcome, will the use of electroacupuncture generate changes in the study of sensory and motor NCV by electrophysiological techniques?

For the question, it is calculated considering the mean and SD resulting at the beginning and end of the intervention of the changes of the NCV of Yanqing Tong et al. of 48.2 ± 0.6 vs 46.2 ± 0.7 (m / s).⁶¹ A comparison of means was made, with the test assumption of a bilateral hypothesis, with a Confidence or Security Level (1- α): 95%, Statistical Power of 80%, Accuracy (d) of 20%, the resulting sample size was:

196 subjects per group

3. For the third outcome, will the use of electroacupuncture generate improvement in the evaluation of the patient's quality of life as measured by the SF36?

So far there is no publication that analyzes the perception of an improvement in quality of life in subjects with diabetic neuropathy with the use of electroacupuncture. Therefore, we have raised the size according to those described in the article by *Kongkiat Kulkantrakorn et al.*⁷⁵ where the aforementioned authors made a "baseline" estimate of the perception of the quality of life of the patient with diabetic foot in 8 domains of the SF-36. Our proposal is that there will be an improvement in the quality of life, in all the domains described, that is, it will be at least equal or better, we have taken into account the average of the physical function which is the deteriorated of 18.9.

Table 4: Comparison of SF-36 mean score in relevant studies

Domains	Multiple sclerosis* (N=85)	Epilepsy* (N=271)	Diabetes* (N=555)	Diabetic foot ulcer [†] (Thailand) (N=40)	Healthy Thai adults [‡] (N=1,345)	PDN current study (N=33) [§]	Current study [§] VS Healthy Thai adults [‡] (P value)
Physical function	33.5	78.9	74.2	18.9	77.3±17.4	31.5±27.7	<0.001 [†]
Role limitation due to physical problem	32.7	60.0	55.1	27.5	82.2±28.6	40.2±39.0	<0.001 [†]
Bodily pain	72.2	72.8	71.7	32.5	75.6±18.4	47.3±30.6	<0.001 [†]
General health	53.7	68.7	52.6	79.5	65.1±18.1	50.8±28.5	0.007 [†]
Vitality	41.9	55.4	54.3	70.9	62.2±13.3	60.9±35.9	0.63
Social functioning	60.2	77.3	81.2	50.9	78.2±18.2	63.6±29.7	0.008 [†]
Role limitation due to emotional problem	59.6	66.3	70.2	51.6	80.4±31.9	42.4±43.5	<0.001 [†]
Emotional well being	67.8	68.4	73.0	36.6	66.1±12.9	39.4±30.7	<0.001 [†]

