*Reference 22; [†]Reference 20; [‡]Reference 8; [§]Current study; [†]Statistically significant; PDN: Painful diabetic neuropathy; SF-36: Short form 36 quality of life questionnaires

Table taken from J Neurosci Rural Pract. 2013 Jul-Sep; 4(3): 267–270.⁷⁵

Making a comparison of averages:

$$n = K [(s1)^2 + (s2)^2] / (M1 - M2)^2$$

K	14.884164	(Za+Zb) ²
s1	7.37	Standard deviation of group 1
s2	27.7	Standard deviation of group 2
m1	31.5	Group 1 Average
m2	18.9	Group 2 Average
n per group=	77	
n total=	154	
Za	2.576	
Zb	1.282	

NOTE: As we discussed previously, we have suggested taking the highest value in order to be sure of having sufficient statistical power and to find all the differences in the proposed mean comparisons of each outcome (that is, the effect of Electroacupuncture compared to sham on the following outcome variables).

Each group was added 20% of the N for possible losses.

OUTCOME VARIABLE	N PER GROUP	ALPHA Z	Z DE BETA	PLUS 20% OF POSSIBLE LOSSES PER GROUP	STUDY TOTAL
Relief of sensory symptoms	30	2.576	1.282	36 Total :36	72
Changes in the study of sensory and motor VCN	109	2.576	1.282	130.8 Total: 131	262
Improvement in quality of life assessment	77	2.576	1.282	92.4 Total: 93	186

The sample of the present study was estimated at 109 for each group, however, 20% was added considering possible losses (each group will be 131), therefore, the total N of the study is 262.

It is important to mention that the way to obtain the sample will be by number of consecutive cases of candidate patients who go to the outpatient consultation of the UMF 20, 41 and 44 of the IMSS of the CDMX, for their subsequent evaluation in the screening and respective randomization in case of being included in the study.

VARIABLES

TABLE 1. CATEGORIZATION OF VARIABLES

	VARIABLE	MEASURING INSTRUMENT	TYPE AND SCALE OF MEASUREMENT	UNITS
DEPENDENT	Sensitive commitment	MDNS	Ordinal qualitative	Normal, diminished and absent
	Brawn	MDNS	Ordinal qualitative	Normal, moderate, severe and absent
	Reflexes	MDNS	Ordinal qualitative	Present, present with effort and absent.
	Sensory symptoms	MNSI	Discrete Quantitative	Dichotomous Response (Yes, No) Evaluation score 13 out of 15
	Aquilian reflex	MNSI	Ordinal qualitative	Present, present with effort and absent.
	Vibration perception	MNSI	Ordinal qualitative	Present, present with effort and absent.
	Pain scale	NRS	Discrete Quantitative	Evaluation score 0-10

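### Does adding 20% to 109 per group leave the trial short of 109 evaluable patients after losses?

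*SAP*

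**What the plan says.** In section A of the SAP (calculation of the sample size), the note above the summary table gives the rule for losses: "Each group was added 20% of the N for possible losses". The NCV row applies it, moving from 109 to "130.8 Total: 131" per group and 262 in total. The closing paragraph repeats the chain. It starts from "The sample of the present study was estimated at 109 for each group" and ends with "20% was added considering possible losses (each group will be 131), therefore, the total N of the study is 262".

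The same rule is used in the other two rows: 30 becomes 36 for symptom relief, and 77 becomes 93 for quality of life. The table's column heading links the 20% to possible losses per group. The section does not express the 20% as an expected proportion of enrolled patients, and it does not state how many evaluable patients should remain.

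**The concern.** Losses come out of the patients enrolled, not out of the base number. A planner who expects to lose a fraction d of those enrolled and wants n left must enrol n/(1 − d). Multiplying by (1 + d) gives a smaller number, and using it in place of the division is a common slip. The SAP multiplies, so it is natural to suspect that slip here.

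At stake would be the enrolment target of 262. If the SAP meant that 109 per group survive a 20% loss, the target would be too low, and the outcome that sets the sample size would be analysed on fewer patients than planned.

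**Working it through.** **Inputs, all from section A of the SAP.** Base for NCV: 109 per group. Allowance: 20% of N added. Enrolled: 131 per group, 262 in total. NCV means and SDs (second outcome): "48.2 ± 0.6 vs 46.2 ± 0.7" m/s. Z values in the summary table: 2.576 and 1.282. Bases for the other outcomes: 30 and 77 per group.

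**1. The SAP's own figure.** 109 × 1.20 = 130.8, rounded up to 131; 2 × 131 = 262. This reproduces exactly. The other rows follow the same rule: 30 × 1.20 = 36, and 77 × 1.20 = 92.4, rounded up to 93.

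**2. What 131 protects.** The largest loss that leaves 109 is (131 − 109)/131 = 22/131 = 16.8%. At a 20% loss, 131 × 0.80 = 104.8 remain, about 105, or 4 short of 109. Keeping 109 after a full 20% loss would need 109/0.80 = 136.25, so 137 per group and 274 in total: 6 more per group and 12 more overall.

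**3. Whether the SAP claims otherwise.** The note describes an addition of 20% of N. The table and the conclusion carry out that addition. Neither says that 20% of those enrolled will be lost, nor that 109 will remain if they are. Step 2 therefore contradicts no statement in the SAP.

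**4. Whether the difference would matter, on the SAP's inputs.**

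- NCV: the standardised difference at 104.8 per group is 2.0/√((0.6² + 0.7²)/104.8) = 22.2, against a critical value of 2.576. Power is effectively 100%.
- Symptom relief: power is above 99.99% at both 109 and 105 per group (two-sided 1% level).
- Quality of life: power is 97.8% at 109 and 97.3% at 105 at the two-sided 1% level, or 99.6% and 99.5% at the 5% level.
- With 131 enrolled, the 77 needed for quality of life are kept up to a loss of 1 − 77/131 = 41.2%, and the 30 for symptom relief up to 1 − 30/131 = 77.1%.

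**5. A deliberately unfavourable assumption.** Suppose that 109 gave exactly the nominal power, which the SAP's NCV inputs do not support. At 104.8 per group, power would be Φ(3.858 × √(104.8/109) − 2.576) = 88.6% instead of 90% at the two-sided 1% level. At the 5% level it would be Φ(2.8016 × √(104.8/109) − 1.96) = 78.4% instead of 80%. Both falls are under 2 percentage points.

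**The case for a change.** The strongest case for the concern is that an allowance for losses has one obvious purpose, which is to have the required number left at the end. The column heading connects the 20% with losses, and the note beside it says that the largest N is chosen so that power is sufficient. A reader could fairly conclude that 109 per group survive a 20% loss, and they would not. One sentence stating the true tolerance of 16.8% would cost nothing. The point would also carry over to another base: 196 × 1.2 = 235.2, rounded up to 236, of which 80% is 188.8, about 7 short of 196.

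The arithmetic in this stands, and so does the remark that the SAP leaves the meaning of the 20% open. What does not follow is that the SAP is wrong. A margin of 20% on the base is a legitimate choice, stated and applied consistently. Dividing by 0.8 answers a different question, one the SAP does not pose. The extra sentence would alter no sample size, analysis or conclusion.

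A second argument is that power may not be as safe as step 4 suggests, because the NCV base itself is in doubt. The text for the second outcome reports "Statistical Power of 80%, Accuracy (d) of 20%, the resulting sample size was" "196 subjects per group", while the summary table gives 109 with Z values that correspond to a two-sided 1% level and 90% power. The SAP's formula with its NCV inputs gives 14.884164 × 0.85/4 = 3.16 per group at those Z values and 7.849 × 0.85/4 = 1.67 at 5% and 80%, so it yields neither 109 nor 196. If 196 were truly required, 105 evaluable patients per group would give only about 54% power (80% design) or 60% (90% design). That is a real defect, but it comes from the conflict over the base. Even with no losses below 109, power would then be only about 55% or 62%, so the loss allowance accounts for very little of the gap.

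**Conclusion.** The concern does not hold. The SAP states that it adds 20% of N, and 109 × 1.2 gives the 131 and 262 that it reports. The figures of 16.8% and about 105 per group are correct descriptions of what that margin covers, but they conflict with nothing the SAP says. Against a 20% loss the difference is about 4 patients per group, with no material effect on power for any of the three outcomes on the SAP's own inputs.

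This rests on two assumptions: that the 20% is read as written, as a margin on the base and not as a forecast loss among those enrolled, and that the printed means and SDs are the planning values. If the first were wrong, the shortfall would still be only those 4 patients per group. The second is tied to the unresolved conflict between 109 and 196, which should be judged as a separate matter and does not turn the stated margin into an error.

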The statistical methods to be used will be two-tailed t-tests for comparison of mean value between groups, paired t-tests will be used for comparison of mean values within groups, and repeated two-way analysis of variance for changes in NCV, pain threshold and glucose concentrations.

To evaluate the degree of association between variables and covariates, univariate and bivariate models will be used using the X² test or Fisher's exact test for discrete variables; or the Student's t test, for continuous variables.

The analysis of these tests will be carried out by means of the Mann-Whitney U statistical test, or by means of ANOVA-type statistical measurement. Correlation studies will be performed by Pearson or Spearman Test.

A multivariate analysis will be carried out including the confounding variables (age, time of evolution of DM, anthropometric and biochemical parameters) using a non-conditional logistic regression model, for discrete dependent variables; and a linear regression model for continuous dependent variables.

The analysis of clinical improvement by means of the MDNS scale, the MNSI and the SF-36 will be performed by means of the Mann-Whitney U statistical test. The analysis of nerve conduction velocities shall be carried out by means of ANOVA-type statistical measurement.

It is contemplated to perform an analysis of multiple results and by subgroups, that is, by stratification according to age, time of diagnosis of DM, degree of affection, scale of pain and type of conventional pharmacological treatment, evaluating sensation and perception of the stimulus of pain, vibration, reflexes, VCN by electrophysiological techniques.

Although both groups may have improvement due to conventional treatment, significant differences or trends in the electroacupuncture group are expected, the analysis will include logistic regression analyzing the confounding variables.

For all tests a value of $p < 0.05$ shall be considered statistically significant.

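### The repeated two-way ANOVA planned for NCV leaves out baseline NCV as a covariate and so gives up precision on the outcome that sets the sample size

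*SAP*

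**What the plan says.** The SAP's closing Statistical Analysis section gives the method for NCV twice. It first lists "repeated two-way analysis of variance for changes in NCV, pain threshold and glucose concentrations". Further on it says: "The analysis of nerve conduction velocities shall be carried out by means of ANOVA-type statistical measurement". Neither sentence mentions the baseline value as a covariate.

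The same section plans a multivariate analysis "including the confounding variables (age, time of evolution of DM, anthropometric and biochemical parameters"), with "a linear regression model for continuous dependent variables". Baseline NCV is not on that list, and the regression is not tied to repeated visits.

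In the sample size section, NCV gives the largest entry of the summary table and so sets the study size: "The sample of the present study was estimated at 109 for each group". For attrition, "Each group was added 20% of the N for possible losses", which brings the study to 131 per group and 262 in total.

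The SAP states neither the number of NCV assessments nor a rule for incomplete patients.

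**The concern.** A repeated-measures ANOVA treats the baseline measurement as one level of the time factor, that is, as an outcome. Before treatment, randomised arms differ only by chance, so baseline is better used to explain variation in the later values. Using it only through a difference assumes a slope of 1 between baseline and follow-up, whereas the actual slope is usually smaller. The contrast is then noisier than it needs to be.

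At stake is precision on the outcome that determines how many patients are recruited. A second, conditional matter is attrition. The SAP expects losses, and the classical form of repeated-measures ANOVA analyses only patients with every visit. If there is an interim visit, patients who miss the last one would contribute nothing.

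**Working it through.** **Inputs from the SAP.** NCV analysed by repeated two-way ANOVA; 109 per group, 131 with the loss allowance; NCV means and SDs "48.2 ± 0.6 vs 46.2 ± 0.7 (m / s").

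**Assumptions, not in the SAP.** Within-patient correlation rho of NCV between visits, 0.5 to 0.9; two or three visits; equal variance s² at each visit.

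**1. The plan's own figures.** The loss step reproduces: 109 × 1.2 = 130.8, rounded to 131, and 2 × 131 = 262. This covers a loss of 22/131 = 16.8%. The 109 does not reproduce: the table's K with the stated means and SDs gives 14.884 × (0.36 + 0.49)/2.0² = 3.2, that is 4 per group, and the text says "196 subjects per group". That is a separate matter. The ratios below do not depend on n, and 109 serves only as the base for translating them into patients.

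**2. Precision with two visits.** The group-by-time test is the t-test on change.
- Variance of change per patient: 2s²(1 − rho).
- Residual variance after baseline adjustment: s²(1 − rho²).
- Ratio: (1 − rho²)/[2(1 − rho)] = (1 + rho)/2.

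| rho | change | adjusted | ratio | patients matching 109 |
|---|---|---|---|---|
| 0.5 | 1.00 | 0.75 | 0.75 | 81.75, so 82 |
| 0.7 | 0.60 | 0.51 | 0.85 | 92.65, so 93 |
| 0.9 | 0.20 | 0.19 | 0.95 | 103.55, so 104 |

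Simulation with 131 per arm and about 17% random loss gave ratios of 0.75, 0.84 and 0.95. If the SDs differ between baseline (s0) and follow-up (s1), the change variance exceeds the adjusted variance by (s0 − rho·s1)². The size of the gain then moves, but apart from one degree of freedom it cannot become a loss.

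**3. What incomplete patients add under random loss.** Three visits, equal correlation 0.5, about 20% random loss: the standard error was 0.139 for completers' change, 0.121 for completers' ANCOVA and 0.120 for the baseline-adjusted likelihood estimate on all observed values. Nearly all the gain comes from the baseline covariate.

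**4. Bias (true effect 0.30 SD, rho 0.5 to 0.9, roughly 17% to 20% loss; in the non-random cases the dependence is in one arm).**

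| Visits and reason for loss | Completers' change | Baseline-adjusted |
|---|---|---|
| Two, random | 0.30 | 0.30 |
| Two, depends on baseline | 0.23 to 0.28 | 0.30 to 0.31 |
| Two, depends on the unseen final value | 0.32 to 0.37 | 0.33 to 0.41 |
| Three, depends on observed interim change | 0.32 to 0.41 | 0.30 to 0.31 |
| Three, depends on observed interim level | 0.30 | 0.30 |

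In the three-visit rows the adjusted estimate uses all observed values. In the last row completers' change is unbiased because the interim value was equally correlated with the first and last visits, so it is unrelated to the change between them. Completers-only ANCOVA was biased there (0.31 to 0.36). With an interim visit, therefore, baseline adjustment should come with use of all observed values.

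**The case against.** The strongest defence is that nothing here is invalid. In a randomised trial the comparison of changes estimates the same effect as the adjusted comparison, and the loss allowance is meant to leave about 109 evaluable patients. The SAP also already plans covariate-adjusted linear regression. This stands in part: the point is about efficiency, not a wrong test. But the regression omits the baseline value of the outcome, which for NCV would ordinarily be the most informative covariate.

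Four stronger readings are tempting, and the SAP does not support them.

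- *A reader might infer that the SAP deletes every patient with a missed visit.* It names a family of analysis, not a missing-data rule. Deletion is a property of the classical procedure, and rules for missing data may be in the protocol.
- *A reader might infer that a mixed model recovers incomplete patients whatever the schedule.* The number of NCV visits is not given. With one post-baseline visit, a patient without the final NCV adds nothing to the adjusted contrast either.
- *A reader might infer that the planned analysis is biased and the alternative is not.* Step 4 shows no difference under random loss and no assured gain when loss depends on unseen outcomes. Nor can a bias be put as a share of the planned effect, which the SAP leaves unsettled: 109 per group with the table's K implies √(2 × 14.884/109) = 0.52 SD, while the stated NCV figures imply 2.0/√0.425 = 3.07 SD.
- *A reader might infer that the test is the group main effect, diluted by the pre-treatment visit.* The SAP speaks of changes and does not designate that effect.

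**Conclusion.** The point holds as one of precision. The NCV analysis omits the baseline value as a covariate, and on a two-visit reading this costs 5% to 25% in variance for rho from 0.9 to 0.5. The size rests on an assumed correlation and on equal variances at the two visits; the direction does not. Keeping patients with a missed visit is an added benefit only if there is more than one post-baseline NCV. A lower bias may be claimed only where dropout depends on observed data (missing at random). The change is worth making before analysis because it is almost free and concerns the outcome on which the trial was sized.

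**What to change.** Replace both NCV sentences in the Statistical Analysis section with one defined model.

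- With one post-baseline visit: ANCOVA of post-baseline NCV on arm, with the baseline value of the same measure as covariate.
- With more than one: a linear mixed model (MIXED in SPSS, the software already named) on all observed post-baseline values, with arm, visit, arm-by-visit and baseline, and an unstructured covariance. The arm contrast at the final visit is the test.

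Use the same approach for pain threshold and glucose. State the number of NCV visits and the missing-at-random assumption, and add a sensitivity analysis for dropout that depends on unseen values.

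The cost is a few lines of SAP text and different SPSS syntax, with no new data, visits or patients. The drawback is that the mixed model's handling of incomplete patients relies on the missing-at-random assumption, which the data cannot verify.

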MEXICAN SOCIAL SECURITY INSTITUTE
EDUCATION, RESEARCH AND HEALTH POLICY UNIT
HEALTH RESEARCH COORDINATION
HIGH SPECIALTY MEDICAL UNIT (UMAE) "DR. BERNARDO SEPÚLVEDA"
CENTRO MÉDICO NACIONAL SIGLO XXI, IMSS, CDMX.
MEDICAL RESEARCH UNIT IN BIOCHEMISTRY.
DEPARTMENT OF NEUROLOGY AND NEUROPHYSIOLOGY.
FAMILY MEDICINE UNITS NUMBER 20, 41 AND 44, IMSS, CDMX.
SPECIALTY OF HUMAN ACUPUNCTURE OF THE ENMH OF THE IPN

Official Title of the study:

“Evaluation of the effect of electroacupuncture on the sensory symptoms of Symmetrical Distal Polyneuropathy of Diabetic origin and its correlation with changes in Nerve Conduction Velocity.”

MEXICAN SOCIAL SECURITY INSTITUTE AND EDUCATION,
RESEARCH AND HEALTH POLICY UNIT STUDY VERIFICATION ID:
R-2020-785-070.
CONBIOÉTICA-09-CEI-009-20160601.

NCT Number: NOT AVAILABLE.

STATISTICAL ANALYSIS
DATE: August 24th, 2022.

A) CALCULATION OF THE SAMPLE SIZE

The calculation of the sample is based on research questions, this is on the effect of electroacupuncture and expected outcomes in relieving sensory symptoms, on changes in sensory and motor VCN and on the patient's quality of life. Therefore, the development of the sample size calculation will be for each outcome variable and in the end the calculations were concentrated in a summary table. We have suggested taking the highest value to be able to have the certainty of having sufficient statistical power and to be able to find all the differences of the proposed average comparisons.

Sample sizes:

1. For the third outcome, related to "relief". Will electroacupuncture be useful in relieving the sensory symptoms produced by PNDs of diabetic origin?

Table 1 of the review of Thakral G et al. (J Diabetes Sci Technol. 2013, 1;7(5):1202-9) was used as a reference, where different reports of the response and usefulness of electrical stimulation as a complementary treatment of painful and sensory diabetic neuropathy were analyzed and compared, according to this analysis the work of Dinesh Kumar et al. (Diabetes Care 1998, 21 (8): 1322-1325). Where we take into account the reported decrease in neuropathic symptoms with the use of electrical stimulation ($66 \pm 10\%$) when compared to a Sham ($55 \pm 12\%$). For the calculation of the N we use the comparison of means. ^{73,74}

	$n = K [(s_1)^2 + (s_2)^2] / (M_1 - M_2)^2$
K	14.884164 (Za+Zb) ²
s1	10 Standard deviation of group 1
s2	12 Standard deviation of group 2
m1	66 Group 1 Average
m2	55 Group 2 Average
n per group=	30
n total=	60

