	Physical function	SF 36	Ordinal qualitative	Excellent, very good, good, regular, bad
	Physical role	SF 36	Ordinal qualitative	Yes, it limits me a lot /Yes, it limits me a little/ No, it doesn't limit me at all.
	Body pain	SF 36	Ordinal qualitative	No, none/ Yes, very little/ Yes, a little/ Yes moderate/ Yes, a lot/ Yes, a lot
	General health	SF 36	Ordinal qualitative	Nothing, a little, Regular, quite, a lot.
	Vitality	SF 36	Ordinal qualitative	Always, almost always, sometimes, only once, never.
	Social function	SF 36	Ordinal qualitative	Always, almost always, sometimes, only once, never.
	Emotional role	SF 36	Ordinal qualitative	Always, almost always, sometimes, only once, never
	Mental health	SF 36	Ordinal qualitative	Totally true, Quite true, I don't know, Quite false, Totally false
	VCN	Electrophysiological techniques (Nicolet, Viking Model IV D, 4 channels)	Continuous quantitative	Latency (ms) Amplitude (mV) Distance (mm) Speed (m/s)
INDEPENDENT	Electroacupuntal points	Zusanli (E36)	Dichotomous qualitative	Dichotomous (Yes, No)
		Fenlong (E40)	Dichotomous qualitative	Dichotomous (Yes, No)
		Yinlingquan(B9)	Dichotomous qualitative	Dichotomous (Yes, No)
		Sanyinjiao (B6)	Dichotomous	Dichotomous

			qualitative	(Yes, No)
		Taichong (H3)	Dichotomous qualitative	Dichotomous (Yes, No)
		Zulinqi (VB41)	Dichotomous qualitative	Dichotomous (Yes, No)
CONFUSING	Age	Years	Discrete quantitative	40-70 years
	Fasting glyceimic control	mg/dl	Discrete Quantitative	100 -180 mg/dl
	Glycosylated hemoglobin concentration	Percentage	Continuous Quantitative	7-10 %
	DM evolution time	Years	Discrete quantitative	5-15 years of evolution
	BMI	Kg/m ²	Discrete quantitative	18-40 Kg/m ²
	Pressure	Mmhg	Discrete quantitative	90/60 mmHg-200/160 mmHg

STATISTICAL ANALYSIS

The collected variables will be integrated into a database in Excel and then analyzed in SPSS (Statistical Product and Service Solutions) for Windows in the 2019 version. The descriptive analysis of the information collected will be carried out using simple and absolute frequencies, as well as measures of central tendency and dispersion. Once the variables have been collected, the Shapiro-Wilk statistic will be applied to determine if their distribution is normal or not.

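### Overlapping between-arm tests with none named as decisive: about 9–10% false positives for nerve conduction velocity if any significant result counts, about 6–9% for the clinical scales

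*SAP*

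**What the plan says.** All the relevant statements are in the SAP, mostly under Statistical analysis, in this order:

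- A normality check after data collection: "the Shapiro-Wilk statistic will be applied to determine if their distribution is normal or not". No consequence is attached to it.
- A general rule that names no outcome: "two-tailed t-tests for comparison of mean value between groups". The same sentence adds paired t-tests within groups and "repeated two-way analysis of variance for changes in NCV, pain threshold and glucose concentrations".
- After a paragraph on association between variables and covariates: "The analysis of these tests will be carried out by means of the Mann-Whitney U statistical test, or by means of ANOVA-type statistical measurement". No rule for choosing is given.
- Linear or logistic regression including the confounding variables.
- An assignment by outcome: "The analysis of clinical improvement by means of the MDNS scale, the MNSI and the SF-36 will be performed by means of the Mann-Whitney U" test. The next sentence gives NCV to an ANOVA-type analysis.
- A closing rule: "For all tests a value of $p < 0.05$ shall be considered statistically significant".

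Under Calculation of the sample size, item 1 (symptom relief) states "For the calculation of the N we use the comparison of means". Items 2 and 3 (NCV and SF-36) are also sized as comparisons of means.

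**The concern.** A reader who follows the section literally obtains more than one between-arm p-value for the same outcome, each with its own verdict at 0.05. NCV has a t-test and a repeated ANOVA, and perhaps a Mann-Whitney test. MDNS, MNSI and SF-36 have a t-test and a Mann-Whitney test. Nothing ranks these tests, so a favourable one could be reported as the result. This raises the error rate within a single outcome, so a correction across the three outcomes would not cure it.

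The endpoint is also loose. The t-test compares mean values, the ANOVA concerns changes, and the Mann-Whitney test concerns *clinical improvement*, which the SAP does not define as a final value or a change. Two tests on different endpoints agree less often than two tests on the same values, so this looseness matters more than the choice between parametric and rank methods.

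**Working it through.** **Inputs from the SAP.** Two-sided 0.05 for every test; 109 per arm before the allowance for losses. The text of sizing item 2 gives 196 per arm for NCV instead. That conflict is a separate matter, and the rates below hardly move between 30 and 131 per arm.

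**Assumptions not in the SAP.** Two visits, equal arms, equal variance at both visits, baseline-to-final correlation ρ of 0.5 to 0.8, no true effect, and an error counted if any of the tests is significant. The regressions are left out.

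**Scale of the sizing.** The SAP's formula is n = K(s1² + s2²)/(M1 − M2)² with K = 14.884164.

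- Relief: 14.884164 × (10² + 12²)/(66 − 55)² = 14.884164 × 244/121 = 30.01 (stated 30).
- SF-36 physical function: 14.884164 × (7.37² + 27.7²)/(31.5 − 18.9)² = 14.884164 × 821.61/158.76 = 77.03 (stated 77).

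Both reproduce, and both are differences in means.

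**Two tests on different endpoints.** With two visits, the group-by-time term of the repeated ANOVA equals a t-test on change. If X is the baseline and Y the final value, corr(Y, Y − X) = √((1 − ρ)/2). In large samples, P(at least one significant) = 0.05 + 0.05 − P(both significant), with P(both) from the bivariate normal distribution:

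| ρ | corr(Y, Y − X) | P(both) | P(at least one) |
|---|---|---|---|
| 0.5 | 0.500 | 0.0093 | 9.1% |
| 0.7 | 0.387 | 0.0065 | 9.3% |
| 0.8 | 0.316 | 0.0051 | 9.5% |

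**Two tests on the same values.** For normal data the t and Mann-Whitney statistics have large-sample correlation √(3/π) = 0.977. The same calculation gives 6.0%.

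**Simulation under no effect, 109 per arm:**

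| Tests counted for one outcome | Chance of at least one p < 0.05 |
|---|---|
| One fixed test | 4.8–5.3% |
| t-test or Mann-Whitney, same values, normal | 5.6–6.2% |
| t-test or Mann-Whitney, same values, skewed or heavy-tailed | 7–8% |
| Final-value t-test or group-by-time ANOVA | 9.0–10.0% |
| Those two or Mann-Whitney on the final value, normal | 9.6–10.9% |
| The same three, skewed or heavy-tailed | 11.0–11.4% |
| Final-value t-test or Mann-Whitney on change | 9.0–10.1% |

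A one-way ANOVA of two groups equals the t-test and adds nothing.

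**Reading.** Going from one test to t-test or Mann-Whitney on the same values adds about one percentage point for normal data. Going from one test to final value or change adds about four. Most of the excess therefore comes from mixing endpoints.

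**The case against.** The strongest reply is that the section resolves itself. Its later paragraph assigns Mann-Whitney to MDNS, MNSI and SF-36 and ANOVA to NCV. That agrees with the repeated ANOVA named earlier and broadly with Table 1, which lists SF-36 and most MDNS and MNSI items as ordinal and NCV as continuous. A specific rule would normally override a general one. The sentence with the unexplained *or* may also refer only to the covariate paragraph just before it.

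Much of this stands: a sensible reader can guess the intended test. But the later paragraph does not withdraw or subordinate the t-tests, the *or* sentence or the regressions. An ANOVA-type analysis is not tied to a group or a group-by-time effect. The NRS pain score in Table 1 is not assigned a test by name. The final value or the change is not chosen for the scales.

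Four stronger readings are tempting, and the SAP does not support them:

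- *Three tests joined by one* or. The word joins only Mann-Whitney and ANOVA; the t-test stands in another sentence.
- *A 10% error rate for every outcome.* The repeated ANOVA is assigned only to NCV, pain threshold and glucose. The scales reach about 9% only on the mixed-endpoint reading.
- *Shapiro-Wilk as a tie-breaker that inflates error.* The SAP ties it to no test choice. If it did decide strictly between t-test and Mann-Whitney, the simulated rate is 4.0–5.9%, with no clear inflation. Its near-certain rejection (98–100% simulated) concerns a rounded 0–10 score, not continuous NCV.
- *Mean differences left unestimated.* The general t-tests do compare means. Only the rank test named for the scales does not estimate a mean difference. Sizing on means and testing by ranks is not in itself an error.

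**Conclusion.** The concern holds in a limited form. The section plans overlapping between-arm tests, all judged at 0.05, with no decisive analysis named. Outside NCV changes, the endpoint is not fixed as final value or change.

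Under the stated assumptions, the false-positive rate is about 9–10% for NCV instead of 5%. For the scales it is about 6%, or 7–8% if skewed, when both tests use the same values, and about 9% if *clinical improvement* means change while the t-test uses the final value. These are rates under selective reporting. The SAP does not say that the best result will be reported; it leaves room for it. If the outcome-specific sentences alone were followed, with one endpoint each, the rate would be the nominal 5%.

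A smaller point also stands: the test assigned to the scales does not return the mean difference on which relief and SF-36 were sized. For relief this rests on an inference that it is read from one of the named scales, because the Statistical analysis section does not name relief as an outcome. The point is of moderate weight and should be settled before the data are analysed.

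**What to change.** For each sized outcome (symptom relief, NCV speed, SF-36 physical function), name one decisive between-arm analysis and one endpoint definition. One example is the difference in means at the final visit with a 95% confidence interval, from a linear model adjusted for the baseline value. For relief, also name the instrument and say whether the endpoint is a percentage reduction, as in the sizing, or a final score.

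Label the t-tests, Mann-Whitney tests and other ANOVA results as sensitivity analyses without a significance verdict. Delete the sentence beginning *The analysis of these tests*, or reconcile it with the outcome-specific sentences. If the sponsor prefers a rank test for a scale treated as ordinal, that is defensible, provided it is the only decisive test and the SAP states which effect estimate accompanies it.

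The cost is a short edit. The sponsor gives up choosing among tests after seeing the data. No change to sample size or data collection is needed.
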